#### SCHEMATIC DESIGN OF THE STUDY:

The FLAME Study is a 16 week, open randomized clinical trial, evaluating the pharmacogenomic predictors of response to treatment and adverse events, of treatment with fluoxetine ( $n=200$ ) and lamotrigine ( $n=200$ ), for bipolar I, II, and bipolar schizoaffective depressed adults (18 to 65). Participants will be recruited over a 5-year period.

Figure 1. Timeline

Biomarkers that predict response or adverse events to treatment; and biomarker targets of response or adverse events to treatment will also be studied.

### **Description of Recruitment Methods:**

#### **How will participants be identified?**

Potential participants will be identified through routine clinical appointments, advertising, and existing lists/databases of individuals interested in being contacted about participation in research studies. The recruitment of this study will be based in Mayo Clinic, Rochester and Lindner Center of HOPE. Mayo Clinic in Rochester will coordinate the recruitment, data collection and analysis. For Mayo Clinic, Rochester, the main recruiting sources will be the Depression Center (Ge2A), Mood Disorders Unit (Ge3W), Adult Psychiatric Acute Care Unit (Ge2E), Primary Psychiatry and Psychology (GeMW), and Tertiary Psychiatry and Psychology (Mayo W11). Also, Mayo Midwest sites including Austin, Albert Lea, and Eau Claire will be considered for referring patients to Mayo Clinic Rochester. We will also be utilizing the Research Match ([www.researchmatch.org](http://www.researchmatch.org)) registry in order to obtain information about bipolar individuals who are interested in participating in research as an additional recruitment resource. Additionally, this study will be listed in [www.clinicaltrials.gov](http://www.clinicaltrials.gov).

#### **How will participants be contacted?**

The participants will be contacted by the Principal Investigator or study staff. Potential participants may be informed of the FLAME study during a routine clinical appointment. If a potential participant is currently hospitalized, permission to approach the individual will be obtained from the consultant providing psychiatric care to that individual. If a participant indicates interest in learning more about the study, a study Principal Investigator, Co-Investigator(s), or Coordinator will either talk with the participant in person or over the telephone to determine interest and eligibility. Potential participants may also come across one of the recruitment materials (listed below) and contact a Study Coordinator or Investigator directly to learn more about the project.

Potential participants identified from lists/databases of individuals interested in being contacted about future research studies they may qualify for may either be contacted via telephone (with an IRB-approved telephone script) or letter mailing (with an IRB-approved contact letter). The recruitment materials for this study include advertising posters and brochures posted in participant and employee waiting areas, physician referrals, and online listing in Mayo's clinical trials website and classifieds. The research team may also request to retrieve diagnosis data from medical records at the Mayo Clinic and Lindner Center of HOPE to compile a list of participants with bipolar disorder type I or II. An invitation to participate letter will be sent to the list of participants. Eligibility will be determined by the principal investigator or a psychiatrist who is a co-investigator by interview with the subject and by consultation of subject's medical record.

### **Participant Population:**

Number of participants (total, each subgroup including anticipated dropouts, screen failures, nonvisible scan data) 1000 total, n=200 lamotrigine participants, n=200 fluoxetine participants.

Site	Anticipated Sample Collection
Mayo Clinic (Rochester and Austin)	400
Lindner Center of HOPE	100

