#### Power Statement:

Assuming a response rate of 50% (i.e. 150 treatment responders and 150 treatment non-responders), and assuming that 1000 independent SNPs will be evaluated and thus a significance level of  $5*10^{-5}$  will be used for analysis, this study will have 80% power to detect odds ratios of 2.90 for SNPs with minor allele frequency of 0.2, or odds ratios of 2.35 for SNPs with minor allele frequency of 2.35.

However, there is a lack of consistency in results from prior studies of association of different genotypes (and GWA studies) in depression response to medication. There are two critical factors that influence the result of pharmacogenomics and genetic-translational studies in general; 1. The number of recruited participants, and 2. A well characterized phenotype (Hennekam and Biesecker 2012). Recent meta-analysis on pharmacogenomics of antidepressants have identified the necessity for more homogeneous phenotypes needed for stronger associations (GENDEP, MARS and STAR\*D Investigators, 2013). Using publically available data from the GAIN consortium, our group has demonstrated that the number of participants needed to find genetic associations in complex phenotypes, when they are homogeneous, can be reduced considerably (unpublished data; Winham, 2013). This study will focus on a strict homogeneous and highly reliable phenotypic classification of participants, both for treatment response and adverse events. In addition, unlike rigorous traditional clinical trials, pharmacogenomics trials benefit from a more "real practice setting" in the sense of including participants with comorbidity and non-ideal treatment panoramas like ours (Mrazek and Lerman, 2011).

We propose to use a pharmacogenomic approach to study the contribution of genetic variation in fluoxetine pharmacokinetic and pharmacodynamic pathways to variation in drug response to lamotrigine and fluoxetine in bipolar depression. The genes in each of the pathways to be studied will be tested, not merely for individual SNPs, but rather by selecting htSNPs for intragene haplotypes for genes that encode proteins which participate in these pathways.

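### The 80% power statement rests on 300 evaluable participants, but the aims are written per drug with 200 each; the totals 1000, 500, 400 and 300 are not linked by any stated rate

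*Combined protocol and SAP*

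**What the plan says.** Participant Population puts the first total under a label that covers several kinds of loss: "Number of participants (total, each subgroup including anticipated dropouts, screen failures, nonvisible scan data) 1000 total". The counts on that line read "1000 total, n=200 lamotrigine participants, n=200 fluoxetine participants", so the two arms make 400. The Abstract, Aims, Hypothesis and Schematic Design sections all repeat 200 per drug. The site table directly below is headed "Anticipated Sample Collection" and lists 400 for Mayo Clinic and 100 for the Lindner Center, 500 in all.

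The Power Statement assumes a 50% response rate and gives the groups as "150 treatment responders and 150 treatment non-responders", 300 in all. It uses a significance level of 0.00005 for 1000 SNPs. It claims 80% power for an odds ratio of 2.90 at minor allele frequency (MAF) 0.2, and for an odds ratio of 2.35 at an MAF that is also printed as 2.35, which is impossible for a frequency.

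Aim 1 and Hypothesis 1 concern response to lamotrigine or to fluoxetine, with 200 participants attached to each drug. Data Analysis specifies logistic regression with a log-additive allele effect and does not say whether the two arms are analysed together.

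**The concern.** The site total of 500 equals neither the 1000 nor the 400 given in the same section, and the power calculation uses a fourth number. The protocol describes ways of losing participants (the early discontinuation criteria, and removal after three consecutive missed visits) but quantifies none of them. A reader therefore cannot trace how many participants per drug are expected to be evaluable.

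That per-drug number decides whether the power claim applies to the primary question. A candidate-gene analysis of response to one drug can use only the participants given that drug. If the claim of 80% was worked out on a number that neither arm can reach, the study would be reported as adequately powered for drug-specific associations when it is not. A null result in one arm would then be given more weight than it deserves.

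**Working it through.** **1. The counts and the losses that would link them**

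- Participant Population: 1000; site table 400 + 100 = 500; arms 200 + 200 = 400.
- Power Statement: 150 + 150 = 300.
- Implied losses: 1000 to 500 is 50%; 500 to 400 is 20%; 400 to 300 is 25%; 1000 to 400 directly is 60%. None of these rates is stated.

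**2. Method**

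Inputs from the plan: log-additive logistic model, 50% response, alpha 0.05/1000 = 0.00005, odds ratio (OR) 2.90 at MAF 0.2. My assumptions: a two-sided 1-df likelihood-ratio test, and Hardy-Weinberg proportions in the whole sample.

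- Genotype frequencies g for 0, 1 and 2 minor alleles: 0.64, 0.32, 0.04.
- Response probability: logit p(x) = a + x ln(OR), with a chosen so that mean response is 50%. For OR 2.90, a = -0.409 and p = 0.399, 0.658, 0.848. Check: 0.64 × 0.399 + 0.32 × 0.658 + 0.04 × 0.848 = 0.50.
- Information per participant: d = 2[Σ g{p ln p + (1-p) ln(1-p)} - ln 0.5] = 0.0802.
- Power = P(noncentral chi-square, 1 df, noncentrality N × d, exceeds 16.45), where 16.45 is the critical value at alpha 0.00005.

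**3. Reproducing the plan's figure**

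At N=300 the noncentrality is 300 × 0.0802 = 24.1 and power is 0.802. The detectable OR at 80% power is 2.89, against the stated 2.90. The second claim, OR 2.35, reproduces at MAF 0.4 with power 0.803, so the printed MAF is probably a misprint for 0.4. The 300 is therefore the actual basis of the power statement and not itself a typing error.

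**4. The same calculation at other numbers**

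| Analysis set | N | Noncentrality (MAF 0.2) | Power, OR 2.90, MAF 0.2 | Power, OR 2.35, MAF 0.4 | Detectable OR, MAF 0.2 / 0.4 |
|---|---|---|---|---|---|
| Both drugs, no loss | 400 | 32.1 | 0.946 | 0.946 | 2.48 / 2.08 |
| Plan's figure | 300 | 24.1 | 0.802 | 0.803 | 2.89 / 2.35 |
| One drug, no loss (100 + 100) | 200 | 16.0 | 0.480 | 0.481 | 3.82 / 2.91 |
| One drug, 25% loss (75 + 75) | 150 | 12.0 | 0.279 | 0.279 | 4.92 / 3.54 |

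**5. Sensitivity**

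If Hardy-Weinberg proportions are assumed in non-responders instead, power for OR 2.90 at MAF 0.2 is 0.959 at N=300, 0.752 at N=200 and 0.518 at N=150. That version does not reproduce the stated 80%, and one arm still falls short of 80%.

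**The case against.** The strongest reply is that the four totals are different counts in a natural order. The 1000 carries a label that includes screen failures and dropouts. The 500 is headed as sample collection, not randomisation, and blood is drawn at the enrolment visit before the randomisation form is submitted, so more people sampled than randomised is plausible. The 400 is the same throughout. The 300 fits an evaluable number after 25% loss, and if the analysis pools the drugs it is conservative, since a pooled 400 would have power of 0.946.

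Most of this stands. A reader might infer that the totals contradict one another, but the documents do not support that: the counts can form a descending sequence, and only the rates are missing. A reader might also apply the ratio 400/1000 to the site total and conclude that only 200 would be randomised. That does not follow. The 40% is defined on the 1000, nothing says the 500 is the same screening-stage count, and 400/500 = 80% reaches the full 400.

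The reply does not rescue the power statement for the per-drug aims. Whatever the 1000 and 500 mean, an arm of 200 cannot contain 300 participants. Pooling is possible but is not stated. It also fits poorly with the aims and with the introduction, which describes different metabolic pathways for the two drugs (UGT enzymes for lamotrigine, mainly CYP2D6 for fluoxetine). A pooled test addresses an allele effect common to both drugs, which is a different question.

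**Conclusion.** The point holds in two parts of unequal weight.

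The main one is that the stated 80% power does not apply to Aim 1 and Hypothesis 1 as written per drug. For an odds ratio of 2.90 at MAF 0.2, per-drug power is about 48% if every randomised participant is evaluable and about 28% after a 25% loss. The detectable odds ratios are about 3.8 and 4.9. N=300 is adequate only for an analysis pooling both drugs.

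The lesser one is that four totals appear without linking rates, and the site total matches neither of the totals beside it. This is a gap in definition. It does not show that 400 is out of reach or that the trial would finish at half its size.

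These results assume a two-sided test, 50% response in each arm, equal arms and Hardy-Weinberg proportions in the whole sample. The 25% loss is inferred from 400 to 300 and is not stated in the plan. The MAF of 0.4 for the second claim is likewise inferred.

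**What to change.** - Restate the Power Statement with the evaluable number per drug, the loss assumed in reaching it, and the detectable odds ratios at that number. If the 300 is meant to pool the drugs, say so and print the per-drug figures beside it.
- State in Data Analysis whether the primary SNP tests are run within each drug or pooled.
- Correct the impossible minor allele frequency.
- In Participant Population, label each count as consented, sampled, randomised (400) or evaluable, by site and by arm where relevant, and give the rate assumed between successive counts. Say which of these the site total of 500 represents.

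The cost is protocol wording, a short recalculation and a less favourable power figure. No extra participants are needed. Keeping 80% power per drug at the stated odds ratios would take 300 evaluable on each drug (2 × 300 = 600). That would be a change of design, which this point does not ask for.

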### **Inclusion Criteria:**

1. Adult participants, age 18-65.
2. Outpatients or inpatients with a diagnosis of bipolar I, II or schizoaffective bipolar disorder, depressed phase, non-psychotic, (DSM-IV criteria, SCID Module A and D confirmed).

3. At least mild symptom severity of depression as defined by the Clinical Global Impression for Bipolar Disorder (CGI-BP, Spearing et al. 1997) >2
4. Antimanic mood stabilization treatment. Bipolar I participants must be on conventional mood stabilizing treatment [lithium, divalproex or valproate, or an atypical antipsychotic]. Participants with Schizoaffective Bipolar Disorder must be on an atypical antipsychotic. Participants with bipolar II disorder may pursue the FLAME Study as monotherapy.
5. Negative urine pregnancy test.
6. Participants not planning pregnancy in the near future (6 months).
7. Negative urine toxicology screen (except cannabis).
8. No evidence of clinically significant laboratory screening tests (complete blood count (CBC); electrolytes; thyroid stimulating hormone (TSH); creatinine/BUN, AST/ALT). Clinical laboratory evaluation within the last three months is acceptable.

**Exclusion Criteria:**

1. Inability or unwilling to provide informed consent.
2. Inability to understand English.
3. Actively suicidal participants at screening or enrollment visit defined as a response of 3 or 4 on question 4 of the Bipolar Inventory of Symptoms Scale (BISS).
4. Active delusions or hallucinations defined as a score of 3 or 4 on the BISS question 40 (persecutory ideas) or 41 (delusions or hallucinations).
5. Impaired insight as defined as a score of 3 or 4 on BISS question 42 (insight).
6. Hypomania defined by a BISS manic subscore of  $\geq 15$ .
7. Actively suicidal patients as defined by any of the following responses to questions from the C-SSRS: "Yes" response to questions 4, "Yes" response to question 5, "Yes" response to questions 1, 2 or 3 with scores of 4 or 5 in any of the intensity of ideation items within the last week. Axis I or II comorbidity that by referring mental health professional and/or study psychiatrist is primary need of treatment (This will be assessed by the site principal investigator, who has  $>10$  years clinical experience with this population. Hospital discharge summaries and outpatient medical records may be reviewed (i.e. adequate trials of mood stabilizing treatments with minimal to no response, prominent self-injurious behavior in the absence of significant mood symptomatology, or atypical cycle patterns) to make this decision).
8. Pregnant participants.
9. Unwilling or unable to taper any current antidepressant therapy.
10. Participants currently breastfeeding.
11. Female not practicing a reliable form of birth control (condom, IUD, depo injection)
12. Due to lamotrigine pharmacokinetics, female subjects wishing to commence oral contraceptive therapy (OCT) within 3 months of enrollment date or anticipate discontinuing OCT during study (stable oral contraceptive therapy exception).
13. History of active substance abuse disorder within the last 3 months (other than caffeine or cannabis).
14. Participants with medical contraindications that preclude lamotrigine or fluoxetine treatment.
15. History of severe adverse reaction to lamotrigine and/or fluoxetine.
16. Current carbamazepine or oxcarbazepine treatment
17. Unstable active medical illness.

**Step-by-Step Schedule****Enrollment and Study Visits****Pre-screening procedures:**

A potential participant will meet with a member of the study team (PI, Co-I, Study Coordinator, or Research Protocol Specialist) to discuss details of the study and to answer any questions a potential participant may have. A telephone script will be used for this purpose and for telephone calls described during the visits.

If a potential participant agrees to participate in the Study, they will then sign the IRB-approved informed consent form.

Once informed consent is obtained, the participant will complete the Comprehension Assessment (CA) to ensure they understand what their role in the clinical trial is. The study team member completing the consent process with the participant will review the responses provided by the participant. Any incorrect responses will be reviewed in detail until the participant understands the nature of the statement -- these reviews will be documented next to the appropriate items on the CA. The completed CA will be stored with the original copy of the participant's informed consent form. The participant will be given a copy of the consent and the CA. Some research activities may occur after the initial participation process described above and the participant will be asked for their permission to be contacted in the future to obtain additional information for the study. These activities include annual computer linkages to a participant's medical record to ensure accuracy of the biobank database, requests to complete additional questionnaires, and requests for additional blood samples. All participants reserve the right to deny any requests for additional survey completion or sample collection.

#### Screening visit

Once informed consent is accepted and signed, the patient will taper off their antidepressants for two weeks and come back for the baseline visit, or if they are not on any antidepressants, the patient will complete the baseline visit the same day as the screening visit. The baseline visit will include an initial structural diagnostic interview will be completed by a member of the study team (PI, Co-I, Study Coordinator, or Research Protocol Specialist) using the SCID, Module A, D, E, and F to confirm the diagnosis of bipolar I, II or bipolar schizoaffective disorder, current depressive episode according to DSM-IV criteria. Additional rating scales and assessments will include:

- a. Bipolar Inventory of Symptoms Scale (BISS)
- b. Clinical Global Impression (CGI-BP),
- c. Actigraph
- d. WHO-5
- e. Bipolar Biobank Participant Questionnaire (BiB-PQ)\*,
- f. Bipolar Biobank Clinical Questionnaire (BiB-CQ)\*,
- g. Moodcheck
- h. Columbia-Suicide Severity Rating Scale (C-SSRS) Assessing for the past 7 days

If a participant was previously enrolled in the 3BD study (IRB 08-00874 Mayo Clinic Individualized Medicine Biobank for Bipolar Disorder), the clinical questionnaire and patient questionnaire will be repeated if the participant was enrolled to 3BD after 6 months from the screening visit or if clinical judgement suggest that there were significant changes in the participants clinical history.

Participants who wish only to participate in the FLAME study can consent to limit their biospecimens for the pharmacogenomics and biomarker research studies stated in this protocol (and destroyed afterwards) or be available for future studies.

Participants will be asked additionally to participate in biomarker epigenetic and metabolomic/proteomic studies; for which they will be asked to donate two additional blood samples at week 2 and 4 of the comparative effectiveness trial.

If time is a concern, the participant will be allowed to take the BiB-PQ with them to complete it; the participant will be instructed to return the BiB-PQ either via mail or in person.

Selected participants may be asked to have their SCID interview audio/videotaped. These participants would be selected by the investigator and would sign a separate consent allowing permission to be taped. This tape would only be identified with the participant's study identifier and kept in a locked file. The purpose of these tapes would be to be used for inter rater reliability and quality assurance across the multi-site project.

If a participant fulfills all inclusion and exclusion criteria and he/she is not on an antidepressant at the screening visit, can continue directly to the enrollment visit and be randomized.

If the participant was on an antidepressant at the time of the screening visit, he/she is willing to discontinue it and it would be clinically reasonable to stop it, then the antidepressant will be tapered off in 1 week. The participant will have to be at least 7 days completely off the antidepressant before randomization. Then, the total number of days from screening to enrollment for these participants will be 14 days.

Patients enrolling in FLAME will also be given the option to participate in a separate study called 1H-MR Spectroscopy Before and After Treatment with Lamotrigine or Fluoxetine in Bipolar Depression (IRB 13-003660). This study is designed to only recruit subjects who participate in FLAME. This study will be conducted in tandem with FLAME.

Enrollment/baseline/randomization visit (could be at the same day of screening visit)

After consent is obtained and eligibility has been confirmed (inclusion/exclusion criteria; SCID, questionnaire ratings and blood drawn), RAVE® randomization case report form (CRF) will be submitted. Randomization will be done using blocking (blocks of 6 participants), and by study site with RAVE® (License) randomization tool. Block randomization will be utilized to assure balance between the 2 treatment arms. BPI disorder participants, who are randomized to fluoxetine and were not receiving any mood stabilizers at the enrollment visit, will be started on a conventional mood stabilizer just after randomization. These participants should be on a mood stabilizer for at least 7 days before starting study medication.

For participants who were tapered off their antidepressant medication, the eligibility criteria will be reassessed at the enrollment/baseline visit, using the BISS, C-SSRS will be performed at all study visits after screening visit and will be used to assess any changes since last study visit, and CGI-BP scales. SCID, CQ and PQ will not be repeated.

After week 16 of the study, a blood draw will be performed to evaluate medication blood-levels (see Biospecimen section below).

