**Short title: The FLAME Study**

**Protocol Version/Date:06/17/2016**

**IRB#: 13-003545**

**PI: [name]. and colleagues.**

### **ABSTRACT:**

This study is part of the Mayo Clinic Bipolar Biobank and Biomarker Development (3BD) Program. This project is supported by the Marriott Family and Foundation.

Depression is the predominant prevailing mood state of bipolar disorder and it is associated with substantial morbidity and mortality. However, in comparison to acute mania, bipolar depression is understudied both from the standpoint of its pathophysiology as well as clinical trials and treatment development. Given the lack of evidence-based guidelines, clinicians and participants enter a treatment phase with little guidance.

The FLAME Study is a 16-week, open randomized comparative effectiveness trial evaluating genomic predictors and biomarkers of response and adverse events to treatment with lamotrigine (n=200) and fluoxetine (n=200) for bipolar I, II and schizoaffective bipolar depressed participants. Participants age 18-65; will be invited to take part of this study. Participating sites include: Mayo Clinic, Rochester and Austin and Lindner Center of HOPE in Mason, Ohio.

It is known that functionally significant genetic polymorphisms of pharmacokinetic and pharmacodynamic pathways can influence individual differences in response to specific medications. We propose to evaluate the contribution of these pharmacogenomic variations to lamotrigine and fluoxetine treatment response and adverse events. We will correlate clinical phenotypes of response and adverse events to treatment with genotype and haplotype variations of drug metabolism, neurotransmitter biosynthesis, (metabolism, storage, release, reuptake), receptor and intracellular signaling—that have been previously implicated to either lamotrigine or fluoxetine drug mechanism of action. These initial steps will be complemented with genome-wide analysis (GWA), pathway analysis and other candidate gene studies.

Based on our results we aim to develop a translational treatment algorithm of bipolar depression that may help individualized treatment for bipolar depression. This algorithm for participants could potentially increase the likelihood of successful treatment interventions, deliver the “right treatment, for the right participant at the right time”, and decrease the number of ineffective treatments and/or risk for serious adverse events.

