#### **1. Subject Safety**

Safety monitoring will be undertaken by a committee integrated by psychiatrists outside of this protocol consisting of: [name] M.D. Chair, Mayo Clinic Arizona; [name]., George Washington University and Director, Bipolar Collaborative Network; and [name]., FRCPC, University of Calgary. The DSMB will meet twice per year by phone with [name] and [name]. The DSMB Board will review enrollment numbers, demographics, serious adverse events, CGI outcomes, and publications based on biobank data. There is no blind so there is no need for unbinding outcome data.

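### A single, published block size of 6 within site, in an open trial, lets recruiters who track past assignments foresee on average a quarter of allocations with certainty

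*Combined protocol and SAP*

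**What the plan says.** Under the enrollment/baseline/randomization visit, the protocol says: "Randomization will be done using blocking (blocks of 6 participants), and by study site". It gives the purpose as: "Block randomization will be utilized to assure balance between the 2 treatment arms". One block size is named. Nothing is said about varying it or withholding it from sites.

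The Participant Population section sets the arms at "n=200 lamotrigine participants, n=200 fluoxetine participants". No allocation ratio is written. The Abstract lists the sites: "Participating sites include: Mayo Clinic, Rochester and Austin and Lindner Center of HOPE in Mason, Ohio". That makes two or three strata, depending on whether Austin is counted separately.

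The Abstract calls the study a "16-week, open randomized comparative effectiveness trial", and the Subject Safety part of the Data & Safety Monitoring Plan says: "There is no blind so there is no need for unbinding outcome data".

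The section on contacting participants has the principal investigator or a co-investigator psychiatrist determine eligibility. The Study Medication section puts the same roles in charge of study drug. The randomisation form goes to the electronic tool only after consent and confirmed eligibility.

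**The concern.** With blocks of one known size, anyone who knows the earlier assignments at a site can work out the end of each block. Here the treatments are open, the strata are few, and those who judge eligibility see the assignments in the course of managing study drug. Under Study Coordination, the principal investigator and coordinator also review recruitment and per-subject side effects every week.

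There is room for judgement about whom to enrol and when. One exclusion depends on a psychiatrist's view of which condition most needs treatment, and patients who taper an antidepressant reach randomisation 14 days after screening. Clinicians also have arm-specific worries: rash on lamotrigine, induced mania on fluoxetine. If a foreseen allocation influenced whether or when a patient was put forward, case mix could differ between arms. Adjustment for listed covariates could not fully repair this, because clinical judgement is not fully recorded.

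**Working it through.** The plan states no predictability figure, so there is none to reproduce.

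**Inputs**
- Block size 6, by site (enrollment/baseline/randomization visit).
- Allocation 3+3 per block: an assumption, inferred from the 200/200 targets and the stated aim of balance.
- Past assignments at the site are known and block starts can be located: an assumption, made possible by the open design and printed size.

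**Certain allocations, fixed blocks of 6**

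There are C(6,3) = 20 equally likely blocks. An allocation is certain once one arm has filled its three places.

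| Position in block | Chance that the allocation is certain |
|---|---|
| 1 to 3 | 0 |
| 4 | 2/20 = 0.10 |
| 5 | 8/20 = 0.40 |
| 6 | 20/20 = 1.00 |

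The sum is 1.5 per block, and 1.5/6 = 25.0%. As a check, the certain share for block size 2m is 1/(m+1), which is 1/4 for m = 3. By block, 60% contain one certain allocation, 30% contain two and 10% contain three.

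**Scaled to the trial**
- 400 in one sequence: 66 complete blocks and 4 over, so 66 × 1.5 + 0.1 = 99.1, or 24.8%.
- Assumed site splits of 320/80 or 200/120/80: 99.0 in each case.
- The site table's own figures of 400 and 100, which add to 500: 99.1 + 24.1 = 123.2, or 24.6%.

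The share hardly depends on the split.

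**Best-guess success, fixed blocks of 6**

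The strategy is always to guess the arm that is behind. Expected correct guesses in a block of 2m are m + 2^(2m−1)/C(2m,m) − 1/2. For m = 3 this is 3 + 32/20 − 0.5 = 4.1, and 4.1/6 = 68.3%, against 50% with no information.

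**Randomly varying blocks of 4, 6 and 8**

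Assumptions: the three sizes are equally likely, and staff know the set of sizes but not the current one.
- Certain allocations: simulation of 200 sequences of 400 gives 2.1%, or about 8 of 400 (0.021 × 400 = 8.4). The same simulation with fixed blocks of 6 gives 24.7%.
- Best guess: the formula gives 2.833 of 4, 4.1 of 6 and 5.329 of 8. The total is 12.26 of 18, or 68.1%. The simulation also gives 68.1%.

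Best-guess success barely moves because the running counts are equal at the end of every block, whatever its size. Guessing the arm that is behind therefore needs no knowledge of block size.

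**The case against.** The strongest case on the other side is that the planned analyses hardly depend on comparable arms. The aims, the hypotheses and the Data Analysis section concern associations of genotype, haplotype and metabolites with response or adverse events. No lamotrigine-versus-fluoxetine test and no drug-by-SNP test is specified, and the power statement covers SNP effects only. For selective enrolment to create a false SNP association within an arm, it would have to follow genotype. Genotyping is described as a study analysis, not as an input to enrolment. The one genotype mentioned as possibly known to clinicians is CYP2D6 poor-metaboliser status, in the dosing rules. This objection stands, and it confines the concern mainly to between-drug comparisons. A reader might infer that the main genetic results are biased, or that the plan relies on showing a marker to act in one drug and not the other. The documents support neither.

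The plan also has safeguards. Assignment is through an electronic tool after eligibility is confirmed, and patients not on an antidepressant may be screened and randomised on the same day, which leaves less time to defer them. These steps hide the list and prevent changes after assignment. They do not stop deduction before a candidate is put forward, and patients who taper do not have the same-day route. The opportunity is reduced but not removed.

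Finally, no resulting bias is quantified. That is correct: the percentages measure predictability, not a shift in response rate or case mix.

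**Conclusion.** The point holds as a modest, cheaply corrected weakness. On average 25% of allocations, about 99 of 400, could be known with certainty in advance. This rests on 1:1 allocation within blocks and on staff who track every earlier assignment at their site and know where blocks begin. With less complete tracking the share is lower.

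A reader might infer that the randomisation was subverted. The documents show only that the design is open to it. The consequence falls mainly on any between-drug comparison made under the comparative-effectiveness label. A reader might also expect varying block sizes to remove guessing. They nearly remove certainty, but leave best-guess success at about 68%.

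**What to change.** In the randomisation tool, use permuted blocks of randomly varying size within site, for example 4, 6 and 8. Replace the block size in the protocol with a sentence saying that sizes vary at random and are held away from recruiting staff. Certain prediction then falls from 25% to about 2%, even if the set of sizes becomes known. Best-guess success should not be presented as improved.

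The cost is a tool setting and one sentence. The documents do not say whether recruitment had begun at this version. If it had, a short amendment applying to future allocations is also needed. Sample size, visits and treatment do not change.
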